**Gansu Provincial Maternity and Childcare Hospital
Statistical Analysis Plan (SAP)**

Project name: A cohort study on the effects of gestational blood sugar management and postnatal nurturing environment on delayed language development in children

Project source: National Clinical Medical Research Center for Child Health and Disease

Responsible person: [name]

Department: Research Center

Principal Investigator: [name]

Research period: December 2022 to November 2025

Version number: 1.0.

Date of version: April 20th, 2023

According to the implementation plan of the "Western Baby Plan" queue, 1.5-2.5-year-old offspring children who have entered the "Western Baby Plan" queue as research objects were surveyed. The language development and family nurturing environment of 2-year-old children using the "Language Development Evaluation S-S Method, Gesell Infant and Toddler Development Scale, and 0-6 Year Old Family Nurturing Environment Evaluation Scale" were evaluated. We investigated the results of blood sugar screening during pregnancy of children's mothers using retrospective cohort study methods, and follow up the blood sugar management effect of pregnant women with abnormal blood sugar before delivery. At the same time, pregnant women diagnosed with abnormal blood sugar during pregnancy are used as research objects to conduct prospective cohort studies: collect standardized epidemiological survey data of the "Western Baby Plan" queue (mainly including general conditions, diet, exercise, environmental factor investigations, etc.), follow up blood sugar control methods at 36-40 weeks of pregnancy, record pre-pregnancy blood sugar control results and neonatal outcomes, collect peripheral blood and umbilical blood during delivery and store them in the mother-infant biological sample library. The study would follow up the growth and development of offspring, and evaluate the language development and family nurturing environment of 2-year-old children using the "Language Development Evaluation S-S Method, Gesell Infant and Toddler Development Scale, and 0-6 Year Old Family Nurturing Environment Evaluation Scale".

Sample size estimation: Referring to delayed language development in children as the disease outcome, the incidence rate (p_1) of delayed language development in the group exposed to high prenatal sugar is 15%, and the relative risk (RR) is 2.0, with a desired significance level (α) of 0.05 and a desired power ($1-\beta$) of 0.90. By plugging in these values into

the formula, it is determined that both the exposed group and the control group require 160 individuals. Considering the possibility of loss to follow-up, the sample size is increased by 10%. The final estimated sample size for the cohort is 356 cases, with a planned investigation of 360 individuals in the blood sugar abnormality specialized disease cohort.

The sample calculation formula for the cohort study collects data information through the electronic medical record system and the Western Children's Health and Disease Cohort Platform, with dual data entry into an Excel database. Differences in the distribution of general conditions of pregnant women are compared using statistical methods such as the chi-square test or Fisher's exact probability test for categorical data (Socio demographic profile, menstrual and reproductive history, indoor environment Environmental factors, Scale indicators etc.), and statistical methods such as the t-test or ANOVA test for continuous data (Check labs (e.g., fasting blood glucose, glycosylated hemoglobin, lipids, liver and kidney function, etc.). After further controlling for confounding factors, logistic regression analysis is used to explore the impact of poor blood sugar management (high prenatal sugar exposure) on delayed language development around 1-2 years of age.

The combined effect of GDM and postnatal environment of the offspring was analyzed using an EXCEL spreadsheet developed by Andersson et al. The additive interaction was evaluated using three indices: relative excess risk due to interaction (RERI), attributable proportion due to interaction (AP), and synergy index (S). If the 95% confidence intervals (CI) of RERI and AP included 0, and the 95% CI of S included 1, it indicated no additive interaction; otherwise, there was an additive interaction.

The regression models were used to screen the effect of maternal GDM and related factors on the delayed language development (DLD) in

offspring. The binomial logistics regression model and the lasso regression model were constructed by using the "rms" and "glmnet" package to analyse risk factors. The nomogram, which based on proportionally converting each regression coefficient to a zero to one-hundred-point scale, was used to screen the effect of maternal GDM and related factors on the DLD. The effect of the variable with the highest β coefficient was assigned one hundred points. The points were added across independent variables to derive total points, which were converted to predicted probabilities. The total scores of each patient were calculated based on the nomogram for clinical prediction. We used the predictive performance of the nomogram was measured by concordance index (C index). Prediction models were validated by plotting calibration curves and using bootstrap method with one thousand replicate samples. The clinical validity of the prediction model was evaluated using decision curve analysis (DCA).

All analyses were performed using SPSS software (SPSS Inc., Chicago, IL, USA, version 21.0) and R version (4.1.3, <http://www.r-project.org/>). The significance level for statistical tests is set at a value of 0.05, the selection criterion for the regression equation is set at a level of 0.05, and the exclusion level is set at 0.10. Missing values are handled according to the default method in SPSS, which means that observations with missing values in the test variables are excluded from the analysis. A p-value of <0.05 indicates a statistically significant difference.

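### The stated inputs need about 371 per group, not 160; 160 fits if 15% is the unexposed incidence, so either the group label or the stated power is wrong

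*Protocol*

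**What the plan says.** The Protocol's sample size estimation paragraph takes delayed language development as the outcome. It states that the incidence of that outcome, denoted p_1, "development in the group exposed to high prenatal sugar is 15%, and the relative risk (RR) is 2.0". The calculation is made "with a desired significance level (α) of 0.05 and a desired power" of 0.90. Putting these values into a formula is said to show that "both the exposed group and the control group require 160 individuals". A 10% allowance for loss follows, and "The final estimated sample size for the cohort is 356 cases", with 360 planned.

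The paragraph gives no incidence for the unexposed group and does not say whether the test is one- or two-sided. The formula is not visible in the text at hand. No other part of the document gives an incidence for either group or a second statement of power.

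**The concern.** The paragraph presents 160 per group as following from the listed inputs. An exposed incidence of 15% with a relative risk of 2.0 fixes the unexposed incidence at 7.5%. A difference of 7.5 percentage points at that level, with 90% power, should need far more than 160 per group.

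This is the document's only power statement. If 15% really is the exposed incidence, a study described as having 90% power would miss a true doubling of risk more than four times in ten, and a null result would be given too much weight. The expected number of cases would also be half of what the other reading implies. That matters for the adjusted logistic regression, the additive interaction indices, and the lasso and nomogram models. If 15% is the unexposed incidence, size and power are sound and only the description is wrong. A reader cannot tell which case applies.

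**Working it through.** **Inputs from the sample size paragraph.** p_1 = 0.15, labelled as exposed; RR = 2.0; alpha = 0.05; power = 0.90; equal groups of 160; loss 10%; final total 356, planned 360. Sidedness is not given, so two-sided is assumed and one-sided is also shown.

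**Formula** (two independent proportions, 1:1, unadjusted):

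n = [z_a × √(2p̄q̄) + z_b × √(p0q0 + p1q1)]² / (p1 − p0)², where p̄ = (p0 + p1)/2, z_a = 1.960 two-sided and z_b = 1.2816.

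**Step 1: reproduce the plan's 160.** Take 15% as the unexposed incidence, so p0 = 0.15, p1 = 0.30 and p̄ = 0.225.
- First term: 1.960 × √0.34875 = 1.1575
- Second term: 1.2816 × √0.3375 = 0.7445
- n = (1.9020)² / 0.0225 = 160.8

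The unpooled (157.6), pooled (162.9) and arcsine (158.7) versions are also close to 160. The loss step agrees: 2 × 160 / 0.9 = 355.6, which rounds up to 356.

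**Step 2: use the inputs as labelled.** p1 = 0.15, p0 = 0.15/2.0 = 0.075 and p̄ = 0.1125.
- First term: 1.960 × √0.19969 = 0.8758
- Second term: 1.2816 × √0.196875 = 0.5686
- n = (1.4445)² / 0.005625 = 370.9, so 371 per group

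That is 742 evaluable, and 742/0.9 = 824.4, so 825 after allowing for 10% loss.

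**Step 3: see whether another convention rescues 160.** With exposed 15% and unexposed 7.5%:

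| Version | n per group |
|---|---|
| Two-sided, 90% power, unpooled | 367.8 |
| Two-sided, 90%, pooled | 373.0 |
| Two-sided, 90%, arcsine | 363.1 |
| Two-sided, 90%, log relative risk | 393.7 |
| Two-sided, 90%, continuity-corrected | 397.2 |
| One-sided, 90% | 302.1 |
| Two-sided, 80% | 277.5 |
| One-sided, 80% | 218.4 |

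Reading 2.0 as an odds ratio, with 15% still the exposed incidence, gives 451 at 90% power. None of these comes near 160.

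**Step 4: power of 160 per group.** Power = Φ{[(p1 − p0)√n − z_a√(2p̄q̄)] / √(p0q0 + p1q1)}.
- 15% v 7.5%: (0.9487 − 0.8758)/0.4437 = 0.164, so 56.5% (68.5% one-sided). With 180 per group and no loss it is 61.6%.
- 30% v 15%: (1.8974 − 1.1575)/0.5809 = 1.274, so 89.9%.

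**Step 5: expected cases with 160 per group.** 160 × (0.15 + 0.075) = 36, against 160 × (0.30 + 0.15) = 72.

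**Step 6: relative risk that 160 per group detects with 90% power, two-sided.** Holding the unexposed incidence at 7.5%, the exposed must be 19.9%, a relative risk of about 2.65. Holding the exposed incidence at 15%, the unexposed must be about 4.4%, a relative risk of about 3.44.

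**The case against.** The strongest reply is that this is a labelling slip. Reading 15% as the unexposed incidence reproduces both 160 and 356, whereas the literal reading reproduces neither. On that view the study is powered as claimed and a few words put it right. The match is good evidence and makes mislabelling the simplest explanation. It is not proof, because the document offers no second figure for either group's incidence and the formula, which might show what p_1 denotes, is not visible. The relative risk or the 160 could also be misstated: a relative risk of about 2.65 against 7.5% would also give 160.

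A second reply concerns the 360. They are described as a cohort with abnormal blood sugar, so they might all be exposed, with controls drawn from the wider birth cohort. With 360 exposed and, as an assumption, 360 controls, power for 15% versus 7.5% would be about 89%. Against this, 356 is exactly 2 × 160 allowing for 10% loss, which makes 360 a total. Even if the alternative were right, it would limit the loss of power but would not explain how the stated inputs give 160.

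Finally, the planned analysis is an adjusted logistic regression, so neither 57% nor 90% is its exact power. That is true, and it applies equally to the plan's own figure.

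**Conclusion.** The point holds and must be fixed. As worded, the inputs require 371 per group two-sided (303 one-sided), more than twice the stated 160, and no usual formula, sidedness or lower power closes the gap. With 15% as the unexposed incidence, 160 per group and the total of 356 both follow. The document does not settle which statement is wrong. Depending on the answer, power for a doubling of risk is about 90% with 72 expected cases, or about 57% with 36. These figures assume an unadjusted 1:1 comparison with 160 evaluable per group, two-sided testing unless stated, and 360 read as the total. The arithmetic of the loss allowance is not in question.

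**What to change.** State the incidence in both groups, the relative risk and the sidedness, and make the sample size and power agree with them. Two versions are consistent:

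- **If 15% is the unexposed incidence:** unexposed 15%, exposed 30%, relative risk 2.0, two-sided alpha 0.05, power 90%, about 160 per group (161 exactly).
- **If 15% is the exposed incidence:** exposed 15%, unexposed 7.5%. Then either restate the power of 160 per group for a relative risk of 2.0 as about 57% two-sided, or give the relative risk detectable with 90% power, about 2.65 against an unexposed incidence of 7.5%.

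The investigators should choose according to the source of the 15%, not according to which version looks better. The cost is a rewrite of one paragraph, and neither version needs extra participants. Under the first, size and power stand as they are. Under the second, the power the study can claim falls.

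### The only planned interaction with the nurturing environment uses GDM, a contrast the 360 mothers with abnormal blood sugar can hardly supply, while their own exposure, poor management, has none

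*Protocol*

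**What the plan says.** The project title concerns "the effects of gestational blood sugar management and postnatal nurturing environment on delayed language development in children". The opening description sets out two components. The retrospective one starts from children aged 1.5 to 2.5 years already in the birth cohort: "We investigated the results of blood sugar screening during pregnancy of children's mothers using retrospective cohort study methods". It is not restricted to mothers with abnormal blood sugar, and no size is given for it. In the prospective one, "pregnant women diagnosed with abnormal blood sugar during pregnancy are used as research objects to conduct prospective cohort studies".

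The sample-size paragraph gives the rate of delayed language development by saying that "the group exposed to high prenatal sugar is 15%, and the relative risk (RR) is 2.0", with alpha 0.05 and power 0.90. It concludes that "both the exposed group and the control group require 160 individuals", adds 10% for loss to reach 356, and closes "with a planned investigation of 360 individuals in the blood sugar abnormality specialized disease cohort".

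The analysis text then uses two exposures:

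- The adjusted logistic regression explores "the impact of poor blood sugar management (high prenatal sugar exposure) on delayed language development".
- The additive-interaction paragraph (RERI, AP, S) begins "The combined effect of GDM and postnatal environment of the offspring was analyzed". The regression, lasso and nomogram paragraphs that follow also take maternal GDM and related factors.

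The document does not say how GDM, abnormal blood sugar, high prenatal sugar and poor management relate to each other, nor who the controls in the sizing are.

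**The concern.** The exposure and the population do not line up across the analyses. Among mothers who all have abnormal blood sugar, quality of management can vary, but GDM status varies little or not at all. The interaction written into the plan is on the second of these. The interaction that this cohort could support, management by nurturing environment, is not planned.

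Three things are at stake. An analyst who follows the text on the 360 alone may find no usable reference group. An analyst who brings in other mothers must choose the population after the fact. A GDM-by-environment result might also be reported as evidence about glucose management, which is a different exposure, and a reader might attach the 360 and the 90% power to it.

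**Working it through.** **1. Exposure and population, analysis by analysis**

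| Analysis | Exposure named | Population named |
|---|---|---|
| Sample size | High prenatal sugar vs control | 360, abnormal-blood-sugar cohort |
| Adjusted logistic model | Poor management, glossed as high prenatal sugar exposure | None stated |
| RERI, AP, S | GDM, with postnatal environment | None stated |
| Regression, lasso, nomogram | Maternal GDM and related factors | None stated |

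The gloss in the logistic sentence links the sized exposure to management. Nothing links either of them to GDM.

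**2. What RERI needs**

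With the first index for GDM and the second for adverse environment:

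- RERI = RR11 − RR10 − RR01 + 1
- AP = RERI / RR11
- S = (RR11 − 1) / [(RR10 − 1) + (RR01 − 1)]

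Every RR is relative to the cell with neither factor (00). Cells 00 and 01 both consist of mothers without GDM. If the cohort has none, RR10 and RR01 cannot be formed and all three indices are undefined. If it has a few, for instance mothers whose abnormal blood sugar is of another kind, the indices rest on a very small reference group that is not normoglycaemic. With poor versus good management as the first factor, all four cells can be filled from within the 360.

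**3. The plan's own sample size**

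Inputs from the sample-size paragraph: 15%, RR 2.0, alpha 0.05, power 0.90, equal groups, 10% loss. Sidedness and the formula are not legible in the text. I assume the pooled-variance two-proportion formula and show both one-sided and two-sided results:

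n = [z_α √(2p̄q̄) + z_β √(p₁q₁ + p₂q₂)]² / (p₁ − p₂)²

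*15% as the control rate (30% vs 15%), two-sided.* p̄ = 0.225.
- n = [1.960 × 0.5906 + 1.2816 × 0.5809]² / 0.15² = 3.6175 / 0.0225 = 160.8, so 161 per group. This matches the stated 160.
- 2 × 160 / 0.9 = 355.6, so 356. This matches too.
- Power at 160 per group: Φ[(0.15 × √160 − 1.1575) / 0.5809] = Φ(1.274) = 0.90.

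*15% as the exposed rate, as labelled (15% vs 7.5%), two-sided.* p̄ = 0.1125.
- n = [1.960 × 0.4469 + 1.2816 × 0.4437]² / 0.075² = 2.0865 / 0.005625 = 370.9, so 371 per group.
- 2 × 371 / 0.9 = 824.4, so 825 in total, against 360 planned.
- Power at 160 per group: Φ[(0.075 × √160 − 0.8758) / 0.4437] = Φ(0.164) = 0.57.

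*As labelled, one-sided.*
- 303 per group; 2 × 303 / 0.9 = 673.3, so 674 in total.
- Power at 160 per group: Φ[(0.9487 − 0.7350) / 0.4437] = Φ(0.482) = 0.68.

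Across pooled, unpooled, simple-pooled, continuity-corrected and arcsine versions, one- and two-sided, the labelled rates need 296 to 398 per group. None comes near 160. The calculation sizes one two-group contrast; no interaction enters it.

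**The case against.** The strongest reply is that the document does not fix the reading on which the mismatch rests. Controls are never defined. High prenatal sugar versus control could mean abnormal versus normal glucose, with normal-glucose mothers drawn from the retrospective component. GDM would then be close to the sized exposure, and the fault would be loose terminology plus the placement of the 360. GDM is also the exposure named in the interaction, regression and nomogram text, whereas poor management appears once as a model exposure, in a sentence about exploring its impact.

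Much of this stands. A reader might infer that the title poses an interaction question the plan leaves unanswered, but the title names the effects of two factors and does not mention interaction. A reader might also infer that the management model is the primary one and that GDM should be demoted. No analysis is labelled main or primary, so that ordering would be a preference.

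The reply does not remove the problem. If GDM is the intended exposure, placing all 360 in an abnormal-blood-sugar cohort leaves little or no contrast, and the component that could supply one is neither sized nor named. On either reading, the population and comparator for RERI, AP and S have to be written down.

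It is also fair to say that the power figures concern which group the 15% belongs to. They would be the same whichever exposure entered the interaction, so they are a separate correction and not a measure of this mismatch.

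**Conclusion.** The point holds as an inconsistency in text the document already fixes, and it should be corrected. The one planned joint analysis with the environment uses an exposure that the cohort of 360 can hardly contrast, and no joint analysis uses the exposure of the adjusted logistic model. The size is one interaction analysis without a named population and one missing. I put no figure on bias or precision, because the document gives no cell sizes or risks. The conclusion assumes that abnormal blood sugar in the cohort's name is mostly or entirely GDM, which is not stated.

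The sizing label is a second, separate error: power at 160 per group is 0.90 for 30% versus 15%, but about 0.57 two-sided or 0.68 one-sided for 15% versus 7.5% as written. A reader might infer that the study is badly underpowered. The document does not establish this, because its 160 is reproduced almost exactly with 15% as the control rate. A mislabelled rate is therefore the likelier explanation, and only the sponsor can confirm it.

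**What to change.** 1. Add RERI, AP and S for poor versus good blood sugar management by nurturing environment within the abnormal-blood-sugar cohort. The sponsor should define poor management in writing before analysis.
2. First check that gestational control is recorded for the 360. The opening description has control methods followed up at 36 to 40 weeks but describes the recorded control results as pre-pregnancy, and the laboratory list gives no time point for fasting glucose or glycosylated haemoglobin. These statements must be reconciled.
3. Keep GDM by environment, in a named population that includes mothers without GDM: either the retrospective component, with its size stated, or both components pooled with a term for component. Name the population for the regression and nomogram models in the same way.
4. Leave the ranking of the two interactions to the sponsor. Report both as estimates with confidence intervals, and state that the 360 and the 90% power cover only the sized two-group contrast. Say who its controls are.
5. Relabel the 15% as the control rate, or restate the power, and state whether the test is one- or two-sided.

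The cost is mostly wording, one definition, one check of the data items and a second run of the interaction analysis. If gestational control was not recorded for the 360, it would have to be retrieved or collected. The downside is that neither interaction carries a power claim.

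### The cohort is sized on a relative risk of 2.0 but its only adjusted main analysis is logistic; add an adjusted risk ratio and risk difference so that the result is on the scale of the design

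*Protocol*

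**What the plan says.** The document is a cohort study plan; its title page calls it a statistical analysis plan. The sample-size paragraph states that "the incidence rate (p_1) of delayed language development in the group exposed to high prenatal sugar is 15" per cent and that "the relative risk (RR) is 2.0", with "a desired significance level (α) of 0.05" and power 0.90. It concludes that "both the exposed group and the control group require 160 individuals", and after a 10% allowance for loss to follow-up, "The final estimated sample size for the cohort is 356 cases".

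The next paragraph gives the analysis. Chi-square, Fisher, t and ANOVA tests compare the women's general characteristics. After adjustment for confounders, "logistic regression analysis is used to explore the impact of poor blood sugar management (high prenatal sugar exposure") on the language outcome. The later modelling text adds binomial logistic and lasso models for risk-factor screening and a nomogram.

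Nowhere does the document name the effect measure to be reported from the main model. No log-binomial model, modified Poisson model or standardised-risk analysis appears. The relative risk occurs only as a sizing assumption.

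**The concern.** In a cohort the risk in each exposure group can be estimated directly, and the only effect size that this plan puts a number on is a ratio of risks. The only adjusted analysis of that effect usually reports a ratio of odds. When the outcome is not rare the two differ, and the odds ratio lies further from 1. The question is how large the effect of poor glucose management is, so a reader who holds the reported odds ratio against the 2.0 used for sizing would be comparing two different scales. An odds ratio of 2.0 would look as if the design target had been met, although the corresponding relative risk is below 2.0.

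**Working it through.** **Inputs, all from the sample-size paragraph.** Outcome rate 15%, labelled as the exposed group; relative risk 2.0; alpha 0.05 (sidedness not stated); power 0.90; 160 per group; 10% loss; 356 in total.

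**Step 1: which pair of rates lies behind 160?** The pooled two-proportion formula is

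n = [z(α/2)·√(2·p̄·(1−p̄)) + z(β)·√(p1(1−p1) + p0(1−p0))]² / (p1−p0)²,

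where p̄ is the mean of the two rates, z(α/2) = 1.960 and z(β) = 1.282.

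- As worded, p1 = 0.15 and p0 = 0.15/2.0 = 0.075, so p̄ = 0.1125. Then n = (1.960·√0.1997 + 1.282·√0.1969)² / 0.075² = 371 per group. One-sided it is 303. Neither is 160.
- With 15% as the control rate, p1 = 0.30 and p0 = 0.15, so p̄ = 0.225. Then n = (1.960·√0.3488 + 1.282·√0.3375)² / 0.15² = 161 per group (158 with unpooled variance). This agrees with 160.
- Total: 2 × 160/(1 − 0.10) = 355.6, rounded up to 356, as stated.

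The stated size therefore reproduces only with 30% against 15%, while the wording gives 15% against 7.5%. Both pairs are carried forward.

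**Step 2: the odds ratio that corresponds to a relative risk of 2.0.** OR = [p1/(1−p1)] / [p0/(1−p0)].

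| Reading | Exposed | Control | RR | OR | OR relative to 2.0 |
|---|---|---|---|---|---|
| As worded | 15% | 7.5% | 2.0 | (0.15/0.85)/(0.075/0.925) = 2.18 | about 9% higher |
| Reproduces 160 | 30% | 15% | 2.0 | (0.30/0.70)/(0.15/0.85) = 2.43 | about 21% higher |

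As a share of the excess over 1, the same figures are 18% and 43%. These describe the same gap and should not be quoted without that label.

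**Step 3: the reverse direction.** RR = OR / (1 − p0 + p0·OR). An odds ratio of 2.0 gives 2/1.075 = 1.86 at a control rate of 7.5%, and 2/1.15 = 1.74 at 15%.

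**Step 4: does the scale affect the size of the study?** These are Wald sample sizes per group, two-sided alpha 0.05, power 0.90.

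- Log relative risk: n = (1.960 + 1.282)²·[(1−p1)/p1 + (1−p0)/p0] / (ln RR)².
- Log odds ratio: n = (1.960 + 1.282)²·[1/(p1(1−p1)) + 1/(p0(1−p0))] / (ln OR)².

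| Rates | Log RR | Log OR |
|---|---|---|
| 15% / 7.5% | 394 | 387 |
| 30% / 15% | 175 | 169 |

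The choice of scale changes the required number by 6 or 7 per group, so it is not a power issue.

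**The case against.** The strongest reply is that nothing here is wrong. The relative risk is a sizing input and not a declared estimand. An adjusted odds ratio is a valid measure in a cohort study and misleads only someone who reads it as a risk ratio. A reader might infer from the sizing that the plan's headline figure will overstate a promised risk measure. The document does not support that: it promises no reporting measure, and it does not say that the odds ratio will be compared with 2.0.

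Three other strong readings also fail.

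- That the outcome frequency is 15% or more: as worded, 15% is the exposed rate and therefore the higher of the two. The larger gap belongs to the 30%/15% reading, which is an inference from the stated 160.
- That the logistic result cannot be set against the relative risk: it can, because standardising the fitted model yields adjusted risks. The nomogram text already converts point totals to predicted probabilities.
- That sizing on one scale and testing on another costs power: Step 4 shows that it hardly does.

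One may add that the choice of measure could sit in a separate analysis plan. That is possible, but this document carries that title itself and fixes the model.

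What stands of the objection is that the test, the model and the sample-size scale need no defence. What it does not remove is that the plan quantifies its target as a relative risk and names no analysis that reports one after adjustment.

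**Conclusion.** The point holds as a cheap improvement to the reporting of the main result. It is not an error in the test or the power. If the odds ratio is set against the design value of 2.0, it would overstate it by about 9% at the rates as worded, or by about 21% at the rates that reproduce 160 per group.

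These figures are for a simple two-group comparison at the assumed rates. The gap in the adjusted analysis depends on the observed risks and the covariates, for which the document gives no values. The conclusion also rests on the odds ratio being what the logistic model is used to report, which is usual but not stated.

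That the worded rates do not yield 160 per group is a separate matter. It is used here only to show why two pairs of rates are needed.

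**What to change.** In the sentence that sets out the main logistic analysis, add that the adjusted risk ratio and adjusted risk difference, each with a 95% confidence interval, will be reported alongside the odds ratio. Both can come from marginal standardisation of the planned model: predict each child's risk as exposed and as unexposed with the covariates held at their observed values, average each set, and take the ratio and the difference. Modified Poisson regression with robust variance is an alternative for the risk ratio. State also that the odds ratio is not to be read as the relative risk of 2.0 used for sizing.

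The cost is a few lines of code in R, which the plan already uses, and a sentence or two of text. No data collection changes. The downside is an extra pair of estimates to present, and a headline ratio that looks somewhat smaller than the odds ratio.

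### The main model reads high prenatal glucose as poor management without naming glucose at diagnosis as a confounder or protecting it from p-value selection, so severity may be reported as a management effect

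*Protocol*

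**What the plan says.** The protocol has no numbered sections, so places are given by content.

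- **Main model** (analysis paragraph after the sample size): the aim is to "explore the impact of poor blood sugar management (high prenatal sugar exposure) on delayed language development". The parenthesis treats the two exposures as one. Adjustment is described only as "After further controlling for confounding factors, logistic regression analysis is used", with no confounder named.
- **Covariate selection** (closing software paragraph): "the selection criterion for the regression equation is set at a level of 0.05, and the exclusion level is set at 0.10". No variable is exempted.
- **Glucose data** (opening study description): the retrospective part uses "the results of blood sugar screening during pregnancy". The prospective part will "follow up blood sugar control methods at 36-40 weeks of pregnancy". Laboratory values ("fasting blood glucose, glycosylated hemoglobin, lipids, liver and kidney function") are listed for univariate comparison, with no timing given.
- **Groups** (sample size paragraph): "both the exposed group and the control group require 160 individuals". The control group is not described further. The 360 planned subjects all belong to the abnormal blood sugar cohort.

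**The concern.** The project title asks about the effect of blood sugar management. A woman's glucose after diagnosis reflects two things: how abnormal it was when found, and how well it was then managed. If poorly controlled women also tend to have had higher screening values, a comparison that does not hold those values fixed mixes the two.

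The plan may or may not offer screening glucose to the model. Even if it does, the 0.05/0.10 rule can discard it. That rule keeps strong predictors and tends to drop moderate ones, which can still bias the exposure estimate.

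At stake is the conclusion. An association produced by severity at diagnosis could be published as harm from poor management.

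**Working it through.** **The plan's own figure.** 160 per group is used below only as the group size. A two-sided 5% test with 90% power for 30% v 15% needs 161 per group (158 with unpooled variance), which matches 160, and 320/(1 − 0.10) = 356. With 15% taken as the exposed rate, as the text labels it (15% v 7.5%), the requirement is 371. That mismatch is a separate matter and does not bear on this point.

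**Assumed inputs (not in the documents).** Half the women are above the median screening glucose (severe) and half below (mild). Management has no true effect. The share of severe women who end up poorly controlled is a, and the share of mild women is 1 − a. The two groups are then equal in size, and the severe share is a in the poor-control group and 1 − a in the better-control group. Risk of language delay is h if severe and l if mild.

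**Step 1: crude contrast.** p1 = a·h + (1 − a)·l; p0 = (1 − a)·h + a·l; RR = p1/p0. False-positive rate = Φ(d/SE − 1.96) + Φ(−d/SE − 1.96), with d = p1 − p0 and SE = √[p1(1 − p1)/160 + p0(1 − p0)/160].

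| a / 1 − a | h v l | p1 | p0 | RR | d/SE | False positives |
|---|---|---|---|---|---|---|
| 70% / 30% | 30% v 15% | 0.255 | 0.195 | 1.31 | 0.060/0.0466 = 1.29 | 25% |
| 70% / 30% | 22.5% v 15% | 0.2025 | 0.1725 | 1.17 | 0.030/0.0436 = 0.69 | 11% |
| 60% / 40% | 30% v 15% | 0.240 | 0.210 | 1.14 | 0.030/0.0467 = 0.64 | 10% |

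**Step 2: a wider range.** With severity RR R, and severe shares s1 and s0 in the poorly and better controlled groups, spurious RR = [1 + s1(R − 1)]/[1 + s0(R − 1)].

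- R = 1.5, shares 50% v 30%: 1.25/1.15 = 1.09.
- R = 3, shares 80% v 20%: 2.6/1.4 = 1.86.

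The design RR is 2.0.

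**Step 3: would the selection rule keep severity?** Put exposure and binary severity in a logistic model. Severity has β = ln{[h/(1 − h)]/[l/(1 − l)]}. Its information is the sum over the two exposure groups of w_s·w_m/(w_s + w_m), where w = n·p(1 − p) for severe (s) and mild (m) women.

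Middle scenario:

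- β = ln[(0.225/0.775)/(0.15/0.85)] = 0.498.
- Poor control: w_s = 112 × 0.1744 = 19.53, w_m = 48 × 0.1275 = 6.12, giving 4.66.
- Better control: w_s = 48 × 0.1744 = 8.37, w_m = 112 × 0.1275 = 14.28, giving 5.28.
- SE = 1/√9.94 = 0.317, and β/SE = 1.57.
- P(p ≥ 0.10) = Φ(1.645 − 1.57) − Φ(−1.645 − 1.57) = 53%.

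In the other two scenarios β/SE is 0.887/0.305 = 2.91 and 0.887/0.286 = 3.10, so severity fails the 0.10 level about 10% and 7% of the time. Simulation of 3,000 studies per scenario gave 53%, 9% and 6%. Moderate confounding is thus the kind most often dropped.

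**The case against.** **Tempting stronger readings.** A reader might infer that screening glucose and control method are left out of the main model. The text does not say so. It adjusts for unnamed confounders, and the laboratory values compared just before could well be candidates. Their use is unspecified, not excluded. A reader might also take the comparator to be well-managed women who differ in severity. The document says only control group and gives no severity data by group, so both are inferences.

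**Dependence on the contrast.** The retrospective part starts from offspring in the wider cohort, and the interaction analysis uses gestational diabetes as the exposure. If the controls are normoglycaemic, screening glucose helps define exposure, and adjusting for it would remove the effect under study. This stands and limits the remedy. The 360-subject abnormal blood sugar cohort suggests a within-cohort contrast but does not settle it.

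**Control method.** Its absence is not clearly an error, since method may be part of management or follow from severity.

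**Size and data.** The false-positive rates describe a crude test with assumed inputs, whereas the plan specifies an adjusted model. Gestational age at diagnosis and post-load values are not shown to be collected. Screening results are named for the retrospective part only. These objections stand.

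**A covariate list can sit in a separate SAP.** That is fair for the list alone. But this document, itself headed as a SAP, fixes two things: the equation of poor management with high glucose, and a selection rule with no exemption. The point rests on those.

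**Conclusion.** The point holds in a limited form. The plan equates high prenatal glucose with poor management, and it neither names glucose at diagnosis as a confounder nor shields it from p-value selection. If the contrast is between poorer and better control among women with abnormal glucose, severity at diagnosis may be reported as a management effect.

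The three main scenarios give a plausible size, not an observed bias: a spurious RR of 1.14 to 1.31 and 10% to 25% false positives at a nominal 5%. The wider range of assumptions runs from 1.09 to 1.86. All are for the unadjusted comparison with no management effect. They apply to the planned analysis to the extent that severity is not offered to the model or is dropped from it. The change should be made; confidence is medium, because the comparator is undefined and no severity data are given.

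**What to change.** - State who the control group is.
- For poorer versus better control within the abnormal blood sugar cohort, force the recorded pregnancy screening glucose, as a continuous variable, into the main logistic model, exempt from the 0.05/0.10 rule. Report this as the management effect.
- Report the model without screening glucose separately, labelled as the association with total high-glucose exposure.
- Do not use the screening-adjusted model for any contrast with normoglycaemic women.
- Add gestational age at diagnosis and post-load values only if they are recorded.
- Show control method descriptively, without adjusting for it.

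**Cost.** Mainly a change of analysis wording. The interval for the management effect will be somewhat wider. Missing values are handled by dropping the observation, so subjects without a screening value would be lost. Availability must be confirmed for the prospective part before the covariate is fixed.
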